8.1.2 Exclusion criteria

- Lack of compliance with any inclusion criteria
- CI user with contralateral hearing equal to or better than 60 dB (PTA measured at 500, 1000, and 2000Hz)
- EAS user (user of an EAS audio processor)
- Implanted with C40X and C40C
- Implanted with an ABI or Split electrode array
- Known allergic reactions to components of the investigational medical device
- Unstable psychological status
- Anything that, in the opinion of the Investigator, would place the subject at increased risk or preclude the subject's full compliance with or completion of the study

8.2 Strategies for Recruitment and Retention

The pro-active recruitment can be performed by identification of potential study participants from the clinic database and invitation of such patients.

Subjects will be enrolled into the study by signing the informed consent upon being properly informed by the investigator. Subjects will retain a copy of the Informed consent form (ICF).

These recruitment activities will be conducted by the PI or delegated site staff.

8.3 Treatment Assignment Procedures

All subjects participating in this study will receive an upgrade to the SONNET 2 and undergo the same test regime (including tests with the SONNET 2 and SONNET audio processor).

8.4 Subject Identification

A subject willing to sign the ICF voluntarily at the screening visit will be considered enrolled into the study.

Thus, each subject will receive a code, which identifies them uniquely on all study related documents. This code constitutes the subject identification number according to the following scheme:

The subject will receive a subject identification number according to the scheme depicted in Table 3. The subject identification number shall be used henceforth to identify the subject on all study related documents.

[figure not shown]

Table 3: Coding of subjects entered into the study after signing and dating the ICF

The subjects of this study won't be replaced unless they are found not compliant with the inclusion/exclusion criteria prior to the first study specific tests. In this case, a non-compliant subject can be withdrawn and replaced. The replacing subject selected in place of a non-compliant one, will undergo the same approval procedure performed for the replaced subject and will receive a new unique identifier code (see section 8.2 for details about the enrolment procedure).

8.5 Early Withdrawal

8.5.1 Reason for Early Withdrawal

The Investigator may decide to withdraw a subject from the study for one of the following reasons upon agreement with MED-EL:

- Health issues (e.g. occurrence of SAEs, subject's death, etc.)
- Further participation would cause an unacceptable risk to the subject
- The subject moved away
- The subject does not comply with the CIP (e.g. s/he does not attend the visits on schedule; she/he does not communicate relevant medical issues to the Investigator, etc.)

In accordance with the Declaration of Helsinki (Fortaleza, 2013), subjects are free to terminate their participation in the study at any time for any or for no reason, without prejudicing their basic right to receive the best treatment available for them.

If a subject decides to withdraw early, he/she must return the SONNET 2 audio processor.

8.5.2 Handling of Early Withdrawal

Withdrawal of any subjects shall be recorded by the Investigator in the appropriate CRF "Early Withdrawal". If a subject decides to withdraw from the study, every effort should be made to contact him/her and to obtain information about the reason(s) for discontinuation and/or any AEs experienced. Subjects withdrawing prematurely won't be followed-up actively unless they suffer from an ongoing AE. In the case of an ongoing AE, the procedure described in section 8.8 of this CIP shall be followed.

8.6 Early Termination or Suspension of the Study

8.6.1 Reason for early termination or suspension of the study

The study may be suspended or early terminated by MED-EL for any of the following reasons:

- Suspicion or recognition of unexpected, significant and/or unacceptable risks for the subjects
- Insufficient adherence to protocol requirements
- Data that are not sufficiently complete and/or evaluable

- Plans to modify, suspend or discontinue the development of the investigational medical device

8.6.2 Handling of Early Termination or Suspension of the Study

The study may be suspended or early terminated either in all or in specific study sites, depending on the circumstances.

If the study is prematurely terminated or suspended, MED-EL will promptly inform the Investigators/institutions, the relevant IEC(s) and NCA(s) of the termination or suspension and state the reason(s) for the termination or suspension.

8.7 Replacement Policy

Subjects withdrawn from the study won't be replaced. Might the minimal sample size to evaluate the primary objective not be reached due to study drop-out or withdrawal, the enrolment is allowed to continue upon reaching the minimum number of subjects needed for such purpose in the analytical population as define in section 7.2.

8.8 Follow-Up Strategy

8.8.1 Premature Discontinuation

This study is designed to be conducted with a CE-marked investigational medical device which will be used solely within the approved indication.

Upon regular conclusion or premature discontinuation of the study, subjects won't be actively monitored unless a subject suffers from an ongoing AE.

Non-device or -procedure-related AEs that are ongoing at the time of a subject's end of active participation in the study will not be followed-up. Ongoing AEs will be recorded as ongoing and lost-to-follow-up at the time of a subject's end of active participation in the study.

Device- or procedure- related (ADEs, SADEs, and USADEs) or SAEs that are ongoing at the time of a subject's end of active participation in the study will be followed-up for a maximum of eight weeks. The PI will schedule a follow-up visit with the subject within the 8 weeks after the end of active participation. The subject may however decline to be followed-up. If the subject declines a follow-up visit, the unresolved AEs will be recorded as ongoing and lost-to-follow-up. Additionally, any unresolved AEs at the time of the follow-up visit will be recorded as ongoing and lost-to-follow-up.

9 STUDY SCHEDULE

Audio Processor	Configuration	Visit 1	Visit 2	Visit 3	Visit 4	Visit 5
		Speech in quiet (S0)	Speech in noise (S0N0 & S0N0T0)	Speech in noise	Subjective Ratings	Subjective Ratings
SONNET	Default SONNET	✓	✓	✓	✗	✗
SONNET 2	OPUS 2	✓	✓	✓	✓	✓
SONNET 2	Default SONNET	✓	✓	✓	✓	✓
SONNET 2	SONNET 2/ Configuration 1 ¹	✓	✓	✓	✓	✓
SONNET 2	SONNET 2/ Configuration 2 ¹	✓	✓	✓	✓	✓
SONNET 2	SONNET 2/ Configuration 3 ¹	✓	✓	✓	✗	✗
SONNET 2	SONNET 2/ Configuration 4 ¹	✓	✓	✓	✗	✗
Questionnaires	SONNET: APSQ HISQUI SSQ	SONNET 2: SONNET 2 ² Questionnaire HISQUI SSQ	SONNET 2: SONNET 2 ² Questionnaire APSQ HISQUI SSQ	SONNET 2: SONNET 2 ² Questionnaire HISQUI SSQ	SONNET 2: SONNET 2 ² Questionnaire HISQUI SSQ	SONNET 2: SONNET 2 ² Questionnaire HISQUI SSQ

1 Details on all SONNET 2 configurations are described in Table 2

2 The questionnaire will be completed for the SONNET 2 in the SONNET default configuration and one of the four SONNET 2 configurations (which will be randomised across subjects).

9.1 Screening and Upgrade Visit (1st study visit)

Potential subjects will be approached and asked for their willingness to participate in the study. If they indicate interest, they will be informed about the study in detail, receive the information and consent form. The investigator will perform a chart review to determine suitability of the subject.

If the subject voluntarily signs the consent and all inclusion/exclusion criteria are fulfilled the subject will be enrolled in the study. Appropriate fitting for the subject's SONNET will be confirmed according to clinical routine and then receive the upgrade to the SONNET 2. The SONNET 2 will be fitted based on the most current clinical map of the subject. Adjustments to the fitting map imported can be made if deemed necessary according to the clinical routine procedures. Adjustments to the fitting maps across the study visits are possible if deemed necessary according to the clinical routine procedures. Clinical maps will be recorded as part of the study.

For the duration of the study, the subject's own audio processor will be stored at the study site, and only be used at the follow-up test intervals by the subjects.

9.1.1 Testing with the current audio processor (SONNET):

- Speech test in quiet
- User satisfaction and subjective rating via questionnaires

9.1.2 Testing with the SONNET 2:

- Speech test in quiet
 - ❖ Set-up as an OPUS 2
 - ❖ Set-up as an SONNET (without new front-end features)
 - ❖ Setting 1: ASC off, mild WNR, mild NR, mild TR
 - ❖ Setting 2: ASC off, mild WNR, strong NR, strong TR
 - ❖ Setting 3: ASC mild, mild WNR, auto NR, auto TR
 - ❖ Setting 4: ASC strong, strong WNR, auto NR, auto TR
- Set the data logging in all configurations to zero
- MAESTRO Export of all SONNET 2 configurations
- Send subject home with two SONNET 2 configurations (randomized across subjects) and make sure data logging is on when the subject is send home
-

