4.8 Fitting

This study will involve fitting sessions in order to set the maps with the various configurations of front-end processing available for the SONNET 2.

Fitting will generally follow the clinical practice at the centre. Particular front-end features will be enabled/disabled for the four configurations.

Table 2 Overview of the different SONNET 2 fitting configurations

Audio Processor	Configuration	ASC	WNR	Beam-former	AGC Compression	AGC Sensitivity	NR	TR
SONNET	Default	N/A	Mild	NAT	3:1	75%	N/A	N/A
SONNET 2	OPUS 2	Off	Off	OMNI	3:1	75%	N/A	N/A
SONNET 2	SONNET (default)	Off	Mild	NAT	3:1	75%	N/A	N/A
SONNET 2	SONNET 2/1	Off	Mild	NAT	3:1	75%	Mild	Mild
SONNET 2	SONNET 2/2	Off	Mild	NAT	3:1	75%	Strong	Strong
SONNET 2	SONNET 2/3	Mild	Mild	Auto (NAT)	3:1	75%	Auto (Off-Mild)	Auto (Off-Mild)
SONNET 2	SONNET 2/4	Strong	Strong	Auto (OMNI-ABF)	3:1	75%	Auto (Off-Strong)	Auto (Off-Strong)

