7 STUDY DESIGN

7.1 Type of Study

This study has been planned as a mono-centric, open label, prospective longitudinal study where each subject acts as his/her own control.

The SONNET 2 is an incremental innovation to the SONNET audio processor with additional front-end processing features which are designed to improve patient performance in specific auditory environments. The study is designed to prospectively follow-up experienced SONNET users who received the SONNET 2. As intra-individual control, subjects will be acutely tested with the SONNET in the same test conditions as with the SONNET 2.

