9.2 Follow-up Visit 1 (2nd study visit)

The first follow-up visit will be scheduled 2 weeks (± 1 week) after the first study visit.

During this visit, fittings of the SONNET and the SONNET 2 or will be confirmed prior to any study test and only adjusted if needed.

9.2.1 Testing with the current audio processor (SONNET):

- Speech test in noise (S0N0)

9.2.2 Testing with the SONNET 2:

- User satisfaction and sound quality rating via questionnaires
- MAESTRO Export of all SONNET 2 configurations including the data logging information
- Speech test in noise (S0N0)
 - ❖ Set-up as an OPUS 2
 - ❖ Set-up as an SONNET (without new front-end features)
 - ❖ Setting 1: ASC off, mild WNR, mild NR, mild TR
 - ❖ Setting 2: ASC off, mild WNR, strong NR, strong TR
 - ❖ Setting 3: ASC mild, mild WNR, auto NR, auto TR
 - ❖ Setting 4: ASC strong, strong WNR, auto NR, auto TR
- Speech test in noise (S0N0T0)
 - ❖ Set-up as an SONNET (without new front-end features)
 - ❖ Setting 1: ASC off, mild WNR, mild NR, mild TR
 - ❖ Setting 2: ASC off, mild WNR, strong NR, strong TR
- Reset the data logging in all configurations
- Send subject home with two SONNET 2 configurations (randomized across subjects) with data logging set to zero

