10.2 Tests/Material

10.2.1 Impedance Field Telemetry (IFT)

A telemetry recording will be performed according to the procedures explained in the MED-EL Fitting Guide. The impedance field telemetry (IFT) recording ensures the proper function of the implant and measures impedances on all electrodes as well as the ground path.

These data form the basis of every clinical map and are necessary to interpret differences between fitting maps.

10.2.2 **Speech testing in quiet**

The Freiburg Monosyllabic test is an open-set monosyllabic word test and is widely used to test adults in German-speaking countries (K.-H. Hahlbrock & Zöllner, 1970; K. H. Hahlbrock, 1970). It consists in total of 20 lists with 20 words each. Each patient shall perform a training starting the actual testing. The results scored in this training session will not be analysed. The test lists will be allocated according to a randomization procedure. The analysis evaluates the number of correctly repeated words in % correct at a fixed presentation level. Speech is presented at 65dB SPL. The test shall be performed in quiet.

10.2.3 **Speech testing in noise**

In this study speech audiometry in noise will be performed using Oldenburger matrix sentence tests (Wagener, Brand, & Kollmeier, 1999a, 1999b; Wagener, Kühnel, & Kollmeier, 1999).

Oldenburger matrix sentence tests are available as measurement modules of the Oldenburger Measurement Application (OMA) (Hörtech GmbH). Matrix sentence tests will be used in the study, due to the sensitivity and applicability in a two-language study. Speech audiometry with the Oldenburger matrix sentence test using speech test material in the national language of the study site.

The test is used to assess the 50% speech-recognition threshold (SRT50 in dB SNR), which is a measure of the level difference at which speech can be identified at half the time in presence of simultaneous masking noise.

The sentences of matrix tests all are composed with the same structure. Test lists with 20 or 30 items are generated from several such sentences. The words are taken in a seemingly random fashion from an inventory (a matrix) of 50 words (10 words per category).

10.2.4 **Subjective user ratings**

10.2.4.1 **Audio Processor Satisfaction Questionnaire (APSQ)**

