11.5 Special Tests/Procedures

11.5.1 Fitting procedure

Appropriate fitting for the subject's SONNET will be confirmed according to clinical routine and then receive the upgrade to the SONNET 2. The SONNET 2 will be fitted based on the most current clinical map of the subject. Adjustments to the fitting map imported can be made if deemed necessary according to the clinical routine procedures. Adjustments to the fitting maps across the study visits are possible if deemed necessary according to the clinical routine procedures. Clinical maps will be recorded as part of the study.

11.5.1.1 *Telemetry (IFT) recording*

Perform a routine telemetry recording as explained in the MAESTRO user guide. There are no parameters to be adjusted. Save the telemetry recording in MAESTRO and rename it according to the following scheme: "*SubjectIDIFT_visit name*".

11.5.1.2 *MCL and THR recording*

The standard fitting procedure as implemented at the study centre as per clinical routine will be used to determine MCL and THR levels. Briefly, THR and MCL levels are measured using verbal feedback from the patient. THR levels may be obtained using an ascending presentation, followed by a standard bracketing procedure. MCLs are obtained through a method referred to as loudness scaling. The level of current is gradually increased, while the patient reports on the level of loudness and comfort. Ideally, MCL levels should also be balanced across the electrode array. Loudness balancing requires comparison on at least two electrodes at a time until all MCLs are perceived as equally loud. After adjusting the parameters according to the subject's needs, save the THR and MCL recording in MAESTRO and rename it according to the following scheme: "*SubjectIDTHRs_visit name*" and "*SubjectIDMCLs_visit name*".

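### Nothing requires the SONNET and SONNET 2 to be tested on the same THR/MCL map, so their comparison can mix a map change with the front-end effect

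*Protocol*

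**What the plan says.** The design relies on each subject being his or her own control. Protocol 7.1 states that "subjects will be acutely tested with the SONNET in the same test conditions as with the SONNET 2". Table 2 (Protocol 4.8) separates the conditions by front-end settings only: AGC compression and sensitivity are the same in every row, and the text adds that "Particular front-end features will be enabled/disabled for the four configurations". THR and MCL levels are not mentioned there.

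On fitting, Protocol 9.1 first has the existing SONNET fitting confirmed and then says: "The SONNET 2 will be fitted based on the most current clinical map of the subject". The next sentence is the permission at issue: "Adjustments to the fitting map imported can be made if deemed necessary according to the clinical routine procedures". Section 11.5.1 repeats this and extends it over time: "Adjustments to the fitting maps across the study visits are possible if deemed necessary according to the clinical routine procedures". At Visit 2, where all S0N0 testing takes place, the fittings of both processors "will be confirmed prior to any study test and only adjusted if needed"; Protocol 9.3 has the same rule for Visit 3.

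On records, Protocol 9.1 says: "Clinical maps will be recorded as part of the study". The MAESTRO exports listed for each visit name the SONNET 2 configurations; the SONNET is not listed.

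The primary comparison is worded in two ways. Protocol 5.1 and SAP 5.1 compare two programs on one SONNET 2: programmed as a SONNET, and setting 1. Protocol 6.1 and 15.1.1, and SAP 9.1 and 11.2.1, compare the SONNET with the SONNET 2.

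**The concern.** A within-subject comparison isolates the front-end features only if everything else about the fitting is alike in the two conditions. A THR/MCL change made on one processor and not on the other is a co-intervention tied to the condition. If it helps the SONNET 2, it pulls the estimate toward non-inferiority and could mask a loss caused by noise reduction or transient reduction. If it hurts, it could hide a true equivalence. Either way, the difference could no longer be read as the effect of the features in Table 2.

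The plan permits this without any deviation being recorded, and the study is open label, so the person who fits the device knows which condition is being adjusted.

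**Working it through.** **1. What a compliant site may do**

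| Point in study | SONNET | SONNET 2 | Rule that the maps match |
|---|---|---|---|
| Visit 1 (Protocol 9.1, 11.5.1) | fitting confirmed | fitted from current clinical map; imported map may be adjusted | none |
| Visit 1 to Visit 2 | stored at the site | worn at home | none |
| Visit 2, all S0N0 tests (9.2) | confirmed, adjusted if needed, before tests | same | none |
| Visit 3, five-loudspeaker test (9.3) | same | same | none |

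A change made to the SONNET 2 map at Visit 1 need not reach the SONNET. At Visit 2 each fitting can be confirmed as it stands, and the two are then tested on different maps.

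**2. Effect on each contrast**

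Observed difference = front-end effect + (map effect in condition A − map effect in condition B).

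- Same-device contrast (Protocol 5.1, SAP 5.1): both programs sit on one SONNET 2 and start from one imported map. A re-fit common to both cancels, and the bracket is zero unless one configuration alone is changed.
- Hardware contrast (Protocol 6.1, SAP 9.1 and 11.2.1): the bracket is zero only if the SONNET carries the same map, or if a map difference happens to have no effect.

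**3. Whether the analysis would catch it**

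SAP 11.2.1 gives a mean difference with a 95% confidence interval and has no covariate, exclusion or sensitivity analysis for unequal maps. The per-protocol definition (SAP 10.2) and the handling of deviations (SAP 13) do not help, because a permitted adjustment is not a deviation. Randomised test order (Protocol 11.6) balances training and fatigue, not a map tied to a device.

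**4. Size**

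Mean bias = f × d, where f is the share of subjects with unequal maps and d is their net mean effect in dB. The documents give neither. What follows is an illustration of sensitivity, not an estimate for this trial.

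The plan's own sample size comes first, since the illustration uses its SDs. Pooled SD = √((1.586² + 1.463²)/2) = 1.526 dB. With a true difference of 0, a 2 dB margin, z = 1.960 and 1.282, and r = 1, N = 2 × (1.526 × 3.242 / 2)² = 12.23, which rounds up to the stated 13.

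SD of the paired difference = 1.526 × √(2(1 − ρ)). For assumed within-subject correlations ρ of 0, 0.5 and 0.8 this is 2.16, 1.53 and 0.97 dB. Suppose the SONNET 2 is truly worse by exactly 2 dB and map changes favour it by a given mean amount. The chance of wrongly declaring non-inferiority (paired t-test, one-sided 0.025) is then:

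| Mean shift (assumed) | n = 13, ρ = 0 / 0.5 / 0.8 | n = 30, ρ = 0 / 0.5 / 0.8 |
|---|---|---|
| 0 dB | 2.5% throughout | 2.5% throughout |
| 0.25 dB | 5.8 / 7.9 / 13.6% | 8.9 / 13.7 / 27.8% |
| 0.5 dB | 11.7 / 19.2 / 40.5% | 23.2 / 41.1 / 78.3% |

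A 0.25 dB shift needs, for example, 0.25 × 1 dB; a 0.5 dB shift needs 0.25 × 2 dB or 0.5 × 1 dB, all in one direction. If directions are mixed, d tends to zero. In the other direction, with no true difference and a 0.5 dB shift against the SONNET 2, power at n = 13 is 63.4 / 90.1 / 99.9%, compared with 86.5 / 99.1 / 100% without the shift.

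**The case against.** The strongest reply is that the primary objective compares two programs on one device from one imported map, so a shared re-fit cancels. That is right for that contrast. It does not settle the matter, because the hypotheses and SAP 11.2.1 name the SONNET against the SONNET 2, and comparison across all processors is a secondary objective anyway.

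A reader might infer that the plan lets single configurations be re-fitted, for instance only those taken home. The documents do not say so. Protocol 4.8 distinguishes configurations by front-end features, and the THR and MCL file names in 11.5.1.2 carry subject and visit but no processor or configuration, which suggests one set per subject per visit. The possibility rests on silence alone.

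A reader might also infer that maps may be altered between tests, or on the SONNET 2 only. At Visits 2 and 3 the text places adjustment before any test and covers both processors. The uneven permission is at Visit 1, where only speech in quiet is tested; it matters for the primary because the changed map can persist to Visit 2.

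Nor is Protocol 10.2.1 an admission that compared maps will differ. It says telemetry data are "necessary to interpret differences between fitting maps", which explains why telemetry is recorded and fits differences over time or between subjects equally well.

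Finally, maps are recorded and SONNET 2 configurations exported, so unequal maps within the SONNET 2 can be detected. That stands, but no analysis uses the record, and the listed exports do not include the SONNET.

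**Conclusion.** The gap is real but narrower than a general claim that the primary result is confounded. The plan permits the SONNET and the SONNET 2 to be tested on different THR/MCL maps, and nothing in the protocol or SAP prevents this or deals with it. The hardware comparison is exposed; the same-device contrast is exposed only if one configuration is changed alone.

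The size is unknown. Subjects have at least 6 months of SONNET experience and later adjustments are made only if needed, so changes may be few, and their directions may offset each other. The illustration shows only that a consistent shift well below the 2 dB margin would matter if the true deficit lay at the margin; its shifts and correlations are assumptions. The documents do not support a statement that the comparison is biased, or by how much. The point merits correction because the permission is explicit, it bears on the within-subject control, and the remedy is cheap.

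**What to change.** Leave whether and how to adjust a map to clinical routine. Change only what keeps the compared conditions alike:

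1. Protocol 9.1 to 9.5 and 11.5.1: state that any adjustment is completed before the first test of the visit, and that all conditions tested at that visit use the same THR/MCL map and differ only in the Table 2 front-end parameters.
2. Protocol 9.2 and 9.3: export the SONNET map together with the SONNET 2 configurations, so that equality can be checked.
3. SAP 11.2.1: pre-specify a sensitivity analysis of the primary comparison without subjects whose maps differ between the two primary conditions at Visit 2.
4. Reconcile which comparator is primary: Protocol 5.1 and SAP 5.1 against Protocol 6.1 and SAP 9.1 and 11.2.1. This decides which pair of maps item 3 checks.

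The cost is a short protocol amendment, one more export at two visits, some map copying when a map has changed (a few minutes, by my assumption), and slightly fewer subjects in the sensitivity analysis. No visits or subjects are added.
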